Arginine is hydrolyzed to ornithine and urea by the enzyme ARG. In mammals, there are two existing ARG isoenzymes: ARG1 and ARG2. The isoenzymes catalyze the same biochemical reaction but they differ in cellular expression, location, and regulation^{25,26}. The human ARG1 is a cytoplasmic enzyme mainly expressed in hepatocytes. It detoxifies ammonia by catalyzing the final step in urea cycle. ARG1 is also expressed in various extrahepatic tissues where it regulates arginine levels and provides ornithine for biosynthetic reactions²⁷. The expression of ARG1 by some cancer cell lines and regulatory immune cells promote the development of an immunosuppressive environment^{23,28}. The immunotolerogenic impact is partly due to the capability of some cells to secrete of ARG1 from intracellular granules into the microenvironment²⁹ (Fig. 10).

ARG2 is found in the outer mitochondrial membrane and in the mitochondrial matrix. It is predominantly expressed in the prostate, brain, kidney, small intestine, and pancreas. The physiological function of ARG2 is still poorly understood compared to that of ARG1^{20,23}. In cancer research, ARG2 expression has been documented in acute myeloid leukemia (AML) blasts, fibroblasts, and various solid cancers such as prostate cancer³⁰⁻³².

Arginase as an immune suppressor

The depletion of arginine by increased ARG expression has emerged as an effective immunosuppressive pathway for the mammalian immune system. The reduction of arginine from the microenvironment can result in impairment of lymphocyte responses to antigens and arginine-deprivation has now proved to be a strategy for cancer cells to induce immune tolerance^{23,25}. This

effect of arginine-depletion on T cells was studied *in vitro* by Rodriguez *et al.* and it was demonstrated that an arginine deficiency directly affected T cell function through a down regulation the main signaling-transduction component of the TCR, the TCR ζ chain (CD3 ζ), in human T cells through mRNA instability. The impairment of T cell function was fully reversed by the replenishment of ARG³³. At this time, T cell suppression have proved to be the main immunoregulatory mechanism of ARG on the tumor environment³⁴.

ARG producing cells

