During administration of the first 3 vaccines, the patient is observed for 30 minutes with measurements of pulse and blood pressure before and after the vaccine is given. The remainder of vaccines can be administered with observation of the patient for 15 minutes. Patients are observed for acute toxicities in the form of allergic reactions, including anaphylactic shock. Allergic reactions and/or anaphylactic shock will be treated per hospital guidelines.

The vaccines are ordered after contact to the project nurse at the clinical experimental unit (KFE) and to the manufacturing unit. (SOP: "Bestilling og håndtering af ARG1-18,19,20 peptid vaccine til patienter i protokol AA1809", appendix 14). When the vaccine is received, the "receipt of transport" is signed. (SOP: "Transport og udlevering af ARG1-18,19,20 peptid og Montanide, AA1809" appendix 15).

If the patient is prevented in attending the planned treatment day, the treatment can be moved to the following Tuesday or Thursday. If the treatment is postponed more than 6 weeks, patients will be excluded.

Criteria for treatment modifications

Delay of treatment

The treatment will be postponed if the patient experiences non-hematological AE grade ≥ 2 , except fatigue and skin related AEs such as local reaction at the injection site. Otherwise the following criteria are applicable:

Blood samples	Criteria
Leukocytes	$< 1,5 \times 10^9$ (grade 3)
Neutrophilic granulocytes	$< 1,0 \times 10^9$ (grade 3)
Thrombocytes	$< 50 \times 10^9$ (grade 3)
Hemoglobin	$< 5 \text{ mmol/l}$ (grade 3)
Creatinine	$> 3 \times \text{ULM}$ (grade 3)
ASAT	$> 5 \times \text{ULN}$ (grade 3)
ALAT	$> 5 \times \text{ULN}$ (grade 3)
Bilirubin	$> 3 \times \text{ULN}$ (grade 3)
Other AEs	
Skin-related AE	$\geq \text{grade 3}$
Fatigue AE	$\geq \text{grade 3}$
All other AE	$\geq \text{grade 2}$

The treatment will be postponed until CTCAE grade < 2 .

Criteria for end of treatment

1. Unacceptable toxicity (see adverse events)
2. Disease progression
3. On patient request
4. Clinical judgement
5. Other anti cancer treatment. However, radiotherapy treatment of to non target lesions is allowed.
6. Pregnancy
7. Delayed treatment

Unacceptable toxicity:

If treatment related AE grade 3-4 is not reduced appropriately within 12 weeks, the treatment will be stopped and the patient is excluded. Shorter delays can occur multiple times with no consequences for the patient or the trial.

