Delayed treatment: The patient is terminated from the study if the treatment is delayed more than 6 weeks. It is the responsibility of the principle investigator to assess the cause of delay and define the time point for the start of the delay. A patient can be delayed several times during the course of treatment without being excluded.

Early termination from the study

Participants, which are excluded from the study, will be referred back to the oncology team from which they came, for standard treatment. Patients that are excluded before the second vaccine will be replaced with new participants.

Concurrent treatment

- Supportive treatment is given based on clinical judgement and should be noted in the patient chart in accordance with existing practice
- Local palliative radiotherapy is allowed

Manufacture of the peptide vaccine

Peptide

For detailed description of peptide mixture production (see SOP “Fremstilling af ARG1-18,19,20 peptid til protokol AA1809” appendix 12.

The peptide sequence:

IO112	→	ARG 171-190; AKDIVYIGLRDVDPGEHYIL	→ARG1-18
		ARG 181-200; DVDPGEHYILKTLGIKYFSM	→ARG1-19
		ARG 191-210; KTLGIKYFSMTEVDRLGIGK	→ARG1-20

Peptides will be provided with above 90 % purity from external producer. Before administration they will be dissolved in sterile water, mixed and sterile filtrated through a 0,22 µm (30 mm Ø) filter.

Producing the peptide vaccine

The final production of the peptide vaccine will take place under GMP approved laboratory conditions (approved by the Danish Medicines Agency) which quality assures a sterile therapeutic product. It will take place in JM702, Herlev and Gentofte Hospital, authority number: 24223.

Montanide ISA 51

Montanide ISA 51 is produced and sold by Seppic INC: www.seppic.com. France. Montanide is delivered sterile and ready for use in ampules of 3 ml. Montanide ISA 51/Vaccine adjuvant is based on vegetable oil. See product resume or link: <http://www.seppic.com/human-health/vaccine-adjuvant/montanide-isa-51-@/1018/view-1042-seproduit.html>

Preparing the vaccine

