Patients included in the trial will have additional blood tests performed compared to patients receiving standard treatment. The amount of blood and the specific procedure when taking a blood sample are not associated with any significant risk. There is a minimal risk of bleeding and infection and pain and bruising can occur in the area.

Tumor biopsies will be taken by experienced doctors, and is not associated with any significant risk; again there is a small risk of bleeding and infection and pain and bruising might also occur in the area.

CT scans and PET-CT scans are not considered a risk based on the low dose radiation. Both full body CT and PET-CT scans give a radiation doses of around 15 milliSievert (mSv), which is about 5 times the annual background radiation^{61,62}. The contrast used can very rarely cause allergic reactions and brief reduction in renal function; therefore patients are screened by standard procedures prior to the examination.

Monitoring of toxicity

Adverse events

Adverse events (AE) are defined as any undesirable experience occurring to a subject during a clinical trial, whether or not considered related to the investigational treatment. All AEs reported spontaneously by the subject or observed by the investigator or his staff will be recorded and described in the patient chart and the electronic Case Report Form (eCRF). The severity and consequences will be recorded for each AE. The severity and relation to the study medication will be assessed in accordance with the guidelines described in the following.

The investigator must attempt to identify all clinical and objective events from patients receiving treatment and determine their relation to the study medication. The investigator determines the relationship between AEs and treatment using the following guidelines:

Grading of adverse events

The severity of an AE refers to the intensity of the reaction.

Events are graded using CTCAE version 4.0. The following scale can be used if this grading is not applicable:

- 1 = light
- 2 = moderate
- 3 = severe
- 4 = life threatening
- 5 = lethal

Patients experiencing AEs will be monitored with the relevant clinical evaluations and laboratory investigations assessed by the attending physician. All AEs must be monitored until satisfactory restitution or stabilization. Results of the monitoring must be recorded in the patient chart and eCRF.

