Abnormal laboratory tests are not to be recorded in the eCRF unless they have caused a clinical event, resulted in termination of the treatment or otherwise meet the criteria of a serious AE (see the following).

Serious adverse events

A serious adverse event (SAE) is to be reported to sponsor within 24 hours and is defined as any medical occurrence or effect that occurs at any dose:

- results in death;
- is life threatening (at the time of the event);
- requires hospitalization or prolongation of existing patients' hospitalization;
- results in persistent or significant disability or incapacity;
- leads to a congenital anomaly or birth defect;
- is a significant medical event

Adverse reactions

An adverse reaction (AR) can be expected if described in the IMPD or the relevant product summary, or unexpected if the grade or severity does not correlate with the product information in the before mentioned documents.

If the AR is unexpected, meets the criteria of a serious adverse reaction (SAR) and is found related to the investigational treatment, it is classified as a suspected unexpected serious adverse reaction (SUSAR). As this is a First in human trial, the SARs are difficult to classify as "expected" or "unexpected." Therefore, SARs will be reported as SUSARs.

Reporting of adverse events and adverse reactions

Investigator reports SAEs, SARs and SUSARs to sponsor within 24 hours. Sponsor reports SARs and SUSARs to the Danish Medicine Agency within 7 days if considered life threatening or fatal, and otherwise within 15 days. Consequences for the study must be reported. Sponsor submits a list annually that summarizes any SARs and SUSARs as well as a report regarding the study patients' safety to the Danish Medicine Agency and the Research Ethics Committee (investigator can report to the Research Ethics Committee as well).

Sponsor submits a final report to the Danish Medicine Agency at the end of the study, with a description of all SAEs, SARs and SUSARs.

The following is not to be reported:

- Deaths caused by the malignant disease or progression
- Hospitalizations or prolongation of current hospitalization caused by the malignant disease:
 - weight loss
 - fatigue
 - electrolyte derangement
 - pain management
 - anxiety
 - palliative hospitalization
 - stay at hospice or terminal care
 - progression of the underlying disease
- Hospitalizations or prolongation of current hospitalization if the sole reason for hospitalization or prolongation is:

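### Delay of treatment: the sentence holds the vaccine for grade 2 non-haematological AEs, but the table below it holds for creatinine, ASAT, ALAT and bilirubin only at values labelled grade 3

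*Combined protocol and SAP*

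**What the plan says.** Three pieces of text under Criteria for treatment modifications, Delay of treatment, bear on this.

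- **The sentence.** "The treatment will be postponed if the patient experiences non-hematological AE grade" 2 or higher, "except fatigue and skin related AEs such as local reaction at the injection site. Otherwise the following criteria are applicable". The last clause introduces the table.
- **The table.** A blood-sample block has eight rows, all labelled grade 3. They are leukocytes, neutrophils, thrombocytes, haemoglobin, creatinine (above 3 times the upper limit, printed as ULM), ASAT and ALAT (above 5 x ULN) and bilirubin (above 3 x ULN). A second block, for other AEs, has three rows: skin at grade 3 or more, fatigue at grade 3 or more, and a catch-all row at grade 2 or more.
- **The restart line.** "The treatment will be postponed until CTCAE grade" is below 2.

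On the length of a hold, Criteria for end of treatment says: "The patient is terminated from the study if the treatment is delayed more than 6 weeks". Early termination from the study adds that patients excluded before the second vaccine are replaced.

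**The concern.** The sentence and the table give different answers for the same result. If the sentence governs, the creatinine, ASAT, ALAT and bilirubin rows have no work to do, because grade 2 has already postponed treatment. If the table governs, the sentence is wrong for these four tests. Two physicians following the protocol in good faith could handle the same grade 2 value differently.

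The immediate stake is whether a vaccine is given or held. A persistent hold also has consequences for the data. Beyond 6 weeks the patient leaves the study, and if that happens before the second vaccine the patient is replaced. Under the table's limits the same patient would not be held and could go on being dosed. The choice of rule can therefore change both exposure and which patients make up the 10.

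The tests involved are not remote from the target. The section on the ARG enzyme says "The human ARG1 is a cytoplasmic enzyme mainly expressed in hepatocytes", and Peptide vaccine safety discusses possible interference with the urea cycle in the liver.

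**Working it through.** There is no planned figure to reproduce, so the check compares the two rules row by row for a **grade 2** result.

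| Table row | Sentence | Table | Agree? |
|---|---|---|---|
| Leukocytes, neutrophils, thrombocytes, haemoglobin (4 rows) | Outside the rule (haematological) | Not held; limit labelled grade 3 | Yes |
| Creatinine | Postpone | Not held; limit above 3 x ULN, grade 3 | **No** |
| ASAT | Postpone | Not held; limit above 5 x ULN, grade 3 | **No** |
| ALAT | Postpone | Not held; limit above 5 x ULN, grade 3 | **No** |
| Bilirubin | Postpone | Not held; limit above 3 x ULN, grade 3 | **No** |
| Skin, fatigue (2 rows) | Excepted | Not held; grade 3 or more | Yes |
| All remaining AEs (1 row) | Postpone | Postpone; grade 2 or more | Yes |

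Count: 4 + 2 + 1 = 7 rows agree and 4 conflict, out of 11. Within the blood-sample block, 4 of 8 rows conflict.

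**Width of the disputed range.** By the table's own labels, grade 2 ends at 3 x ULN for creatinine and bilirubin and at 5 x ULN for ASAT and ALAT. The documents do not give the lower end of grade 2, so the width cannot be stated.

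**Does a laboratory value count as an AE?** The sentence applies only to AEs. The section Adverse events says "Adverse events (AE) are defined as any undesirable experience occurring to a subject during a clinical trial", whether or not related to treatment, and does not exclude laboratory findings. The delay table also heads its second block as other AEs, which suggests that the blood-sample rows above it are AEs too.

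**Link to eligibility.** Inclusion criterion 10a admits AST and ALT up to 5 x ULN in patients with liver metastases, the same figure as the table's limit. Suppose part of that range is grade 2 and a value present at entry is treated as an AE; both are assumptions. Such a patient would then be eligible, yet held by the sentence at the first vaccine and not held by the table.

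**The case against.** The best defence is that the table is a deliberate carve-out. The sentence's two exceptions, fatigue and skin, are the same two that sit above the catch-all row in the other-AEs block, so the sentence can be read as a summary of that block alone. "Otherwise the following criteria are applicable" would then pass laboratory values to their own rows. The exclusion table under Unacceptable toxicity has a similar layout: separate blood-sample limits, then a catch-all at a lower grade. On this reading the table is consistent within itself and the fault is loose wording.

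This is plausible, and it may be what was intended. It does not rescue the sentence, which lists its exceptions and leaves these four tests out. Read plainly, the linking word covers only what the sentence has not already dealt with.

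A second defence is the recording rule: "Abnormal laboratory tests are not to be recorded in the eCRF unless they have caused a clinical event", or led to termination of treatment or met the seriousness criteria. An isolated grade 2 value might therefore never be handled as an AE. But that rule governs what is entered in the eCRF. It does not exempt a value from the postponement rule.

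Some stronger readings may tempt a reader, and the documents do not support them.

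- *The restart line shows that the sentence governs.* It does not. The same line applies to the haematological, skin and fatigue rows, which also hold at grade 3 and restart below grade 2 without conflict.
- *The table expressly allows dosing at grade 2.* It only fails to trigger a hold, and the investigator may stop treatment on clinical judgement at any time.
- *The primary endpoint itself is at issue.* That endpoint is adverse events by CTCAE together with laboratory monitoring. Grade 3-4 events are the stopping and safety criterion.
- *A fixed number of extra vaccines is at stake.* With dosing every 3 weeks, 6 / 3 = 2 intervals, but doses fall due at weeks 0, 3 and 6. The count is two or three depending on whether the held dose is included, and the principal investigator defines when a delay begins.
- *An effect of the vaccine would show first in these tests.* The protocol names the urea cycle as a potential concern and then argues that harm is unlikely. It does not name these tests as the signal, and creatinine is not a liver test.

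**Conclusion.** The inconsistency is real and is confined to four rows. For creatinine, ASAT, ALAT and bilirubin, a grade 2 value handled as an AE meets the sentence's postponement trigger and not the table's. The text does not say which prevails.

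Its reach is at most these four tests at up to 16 dosing visits per patient. That counts opportunities and is not an expected frequency. The documents give neither a rate of grade 2 values nor the lower bound of grade 2.

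The conclusion rests on one assumption, that a grade 2 laboratory value is an AE for the purpose of the delay rule. The AE definition supports this and no passage contradicts it. The point calls for correction because it concerns a dosing rule in a small first-in-human trial and can alter who stays in. It does not undermine the design.

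**What to change.** Reconcile the sentence and the table under Delay of treatment so that creatinine, ASAT, ALAT and bilirubin each have one postponement criterion. Either add the four tests to the sentence's listed exceptions, or change the four rows to match the sentence. It would also help to state whether an isolated laboratory value counts as an AE for this rule, given the separate limit on eCRF recording. Which threshold applies is for the sponsor and investigator to decide.

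The cost is one sentence or four table cells in an amendment. No visit, test or analysis needs to be added.

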The patient will be excluded subject to the following toxicities:

Blood sample	Criteria
Leukocytes	$< 1,0 \times 10^9$ ($\geq \text{grade 4}$)

Neutrophilic granulocytes	< 0,5 x 10 ⁹ (\geq grade 4)
Thrombocytes	< 25 x 10 ⁹ (\geq grade 4)
Hemoglobin	< 4 mmol/l (\geq grade 4)
Creatinine	>4,5 x ULM (\geq grade 4)
ASAT*	>8 x ULN (\geq grade 4)*
ALAT*	>8 x ULN (\geq grade 4)*

Other Adverse Events	
Bronchospasms or hypersensitivity reactions	\geq grad 3
Skin related AE	\geq grad 4
All other AE	\geq grad 3
Any eye pain or reduced visual of grade 2 or above with no restitution within two weeks will lead to exclusion	

*ASAT/ALAT grade 3 with bilirubin > 1,5 x ULN

** Bilirubin > 3 x ULN with ASAT/ALAT > 2,5 x ULN

Disease progression: Treatment is terminated if disease progression occurs according to RECIST 1.1 at predefined evaluation time points.

Patient request: The treatment can be stopped at any time if the patient wishes so.

Clinical judgement: The treatment can be stopped because of medical conditions at any time if the investigator finds it in the patients' best interest.

Other treatment: Patients will be excluded at any time if a new treatment with an experimental drug or other systemic anticancer treatment is initiated after inclusion in this protocol. The patient will be excluded if systemic treatment with corticosteroids is initiated unless it is on vital indication and in agreement with the physician responsible for the protocol. Supportive treatment is given on usual medical indication and is to be specified in the patient chart and flow sheets.

Pregnancy: A pregnancy test is to be performed before women of childbearing potential can be included in the study. Women of childbearing potential are to contact investigator immediately if pregnancy is suspected (absent or delayed menstruation etc.) at any point during the course of treatment and for 3 months after the end of treatment. A pregnancy test is performed if pregnancy is suspected and the participants can receive no more vaccination treatments and is terminated from the study if it turns out positive. A pregnant participant and the course of the pregnancy will be followed closely in the outpatient clinic.

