The peptide mixture and Montanide is delivered to the dept. of hematology shortly before use by a project nurse or laboratory staff from Hematologic Laboratory 54P4. The peptide mixture constitutes 500 µl consisting of 100 µg ARG1-18, 100 µg ARG1-19, 100 µg ARG1-20 dissolved in a watery solution. Montanide ISA-51 also constitutes 500 µl and just before injection, the two solutions are mixed through an I-connector Luer lock into a 1 ml syringe. The vaccine preparation is marked with patient name, personal security number, date and time of preparation.

For detailed description of the peptide preparation see SOP "Klargøring af ARG1-18,19,20 peptidvaccine til protokol AA1809." appendix 13. See also example of labels for the vaccine in "Eksempel på forsøgsslægemiddeletiketter" appendix 06.

Microbiological control

Endotoxin and cultivation tests of the peptide preparations are performed at the Department of Clinical Microbiology, Herlev and Gentofte Hospital before use of the vaccines.

Evaluation

Data registration

The patients are given a patient number at inclusion in the study to secure patient anonymity. Clinical personal and selected persons in the laboratory will have access to patient information, but only in form of personal ID and name, to secure proper treatment.

The principal investigator has access to patient charts to obtain information regarding the cancer disease to be able to compare this information with the project specific analysis performed on cancer tissue and blood tests.

All relevant data is registered in case rapport form in collaboration with the clinical research unit (KFE). The principal investigator is responsible for manufacturing of the case report form (CRF) and data registration in the CRF after the course of treatment. CRFs will be reported to sponsor.

Sponsor and principal investigator are responsible for data analysis on all included participants. Participant data and CRF will be kept for 5 years in accordance with current guidelines for storage of sensitive data. Completion of a final report will be done in collaboration between the members of the project group.

The analysis will include:

1. Adverse events registration
2. Immunological response
3. Clinical endpoints

Sensitive data and any other remaining samples will be anonymized at the end of the trial.

Following an approval from the Danish Data Protection Agency the Danish biotech company IO Biotech will gain access to pseudonymized trial data.

Monitoring

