Monitoring of the trial will be done by the GCP unit at the University of Copenhagen. It is expected that the responsible GCP unit will contact and visit the principal investigator on a regular basis and request for access to monitoring of the different source documents in relation to the trial (Case Report Forms and other relevant documents).

Audit from the Danish Medicines Agency and other health authorities are likewise allowed on request. Monitor has access to laboratory test results and other participant information needed to verify the entries made in the Case Report Forms. The principal investigator (or his/her substitute) agrees to cooperate with the monitor so that potential problems discovered during the monitoring process will be solved.

Statistical considerations

The study is a phase I trial with the primary objective to evaluate safety of the combination therapy. Since the trial is a first in human study, a formal sample size calculation cannot be performed. From experience with similar studies, it is deemed appropriate to include 10 participants.

Ten participants are deemed sufficient to evaluate safety and considered safe if less than 20 % experience grade 3-4 AE.

All participants that are included and treated according to the protocol will be included in the statistical analyses. Participants who are excluded before receiving treatment will not be included in the statistical analyses:

- Where the inclusion criteria at baseline are not fulfilled
- Patients withdraw their consent
- Have started other treatment

For immunological responses, the 95 % confidential interval will be calculated for patient data and for response rates descriptive statistics will be used.

Effect parameters

Primary effect parameter

Primarily, safety and tolerability of the combination therapy is assessed. This is done by registration of all adverse events and possible unwanted events that occur in relation to the

treatment and in accordance with the CTCAE criteria. Data collection will take place in accordance with the data source list.

Secondary effect parameter

For the assessment of the immunological response, ARG1-specific T cells responses will be identified by the use of ELISPOT technology and antigen specific populations will be characterized for their cytokine secretion pattern.

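### The plan's only analysis set does not clearly keep every vaccinated patient in the safety result, and with ten patients one omission can turn the verdict to safe

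*Combined protocol and SAP*

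**What the plan says.** Statistical considerations gives the only analysis set in the document: "All participants that are included and treated according to the protocol will be included in the statistical analyses". It applies to all analyses without distinction. The next sentence names who is left out: "Participants who are excluded before receiving treatment will not be included in the statistical analyses". Three reasons follow: unmet inclusion criteria, withdrawn consent, or other treatment started. What counts as treatment in line with the protocol is not defined, and there is no separate safety set of all dosed patients.

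The same section sets the safety verdict. The vaccine is "considered safe if less than 20 % experience grade 3-4 AE", and on size "it is deemed appropriate to include 10 participants".

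Three other places bear on who counts:

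- Data registration: "Sponsor and principal investigator are responsible for data analysis on all included participants".
- Criteria for end of treatment uses the word excluded for patients already being vaccinated, for listed toxicities and for starting other therapy. One example is "The patient will be excluded if systemic treatment with corticosteroids is initiated", with an exception for vital indication agreed with the responsible physician.
- Early termination from the study replaces patients excluded before their second vaccine. Such a patient may have had one dose. Nothing says whether that patient stays in the safety result.

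**The concern.** Safety is the primary objective of this first-in-human trial, and its conclusion rests on one proportion with a hard cut-off. The numerator and denominator therefore have to be fixed before any data are seen. The text names two groups: those treated in line with the protocol, who are in, and those excluded before treatment, who are out. A vaccinated patient with a deviation, for example one found ineligible after the first dose, is in neither group with certainty. A patient excluded and replaced after one dose is in the same position, because the protocol uses the same word, excluded, before and after dosing.

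If this is settled only once events are known, the choice can decide the verdict. The early stopping rule gives no protection here. It needs three or more patients with drug-related grade 3-4 events (Study design), and the sensitive case has two.

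**Working it through.** **Inputs.** From Statistical considerations: n = 10, and the vaccine is safe if x/n < 0.20, where x is the number of patients with a grade 3-4 event. There is no sample-size calculation to reproduce, because the plan states that "a formal sample size calculation cannot be performed". The number of vaccinated patients who might be left out is not given, so it is treated below as an assumption with a range.

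**Step 1: the rule at n = 10.** x/10 < 0.20 holds only for x = 0 or 1. Two events give 2/10 = 20.0 %, which is not below 20 %.

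**Step 2: leave out one vaccinated patient (n = 9).**

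| Events in 10 | Verdict on 10 | Event patient left out | Non-event patient left out |
|---|---|---|---|
| 0 | safe | not possible | 0/9 = 0.0 %, safe |
| 1 | safe | 0/9 = 0.0 %, safe | 1/9 = 11.1 %, safe |
| 2 | not safe | **1/9 = 11.1 %, safe** | 2/9 = 22.2 %, not safe |
| 3 | not safe | 2/9 = 22.2 %, not safe | 3/9 = 33.3 %, not safe |

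One omission changes the verdict in a single cell: exactly two events, and one of those two patients left out. The change is towards safe. The evidence barely differs between the two results: the exact (Clopper-Pearson) 95 % intervals are 2.5 to 55.6 % for 2/10 and 0.3 to 48.2 % for 1/9.

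**Step 3: how often the sensitive case arises.** With independent patients and true event rate p, P(X = 2) = 45 p²(1 − p)⁸. Suppose exactly one vaccinated patient is left out. If that patient always has an event whenever one exists, the chance of a changed verdict is P(X = 2). If that patient is picked at random, it is P(X = 2) × 2/10.

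| True rate p | P(X = 2) | × 2/10 |
|---|---|---|
| 10 % | 0.194 | 0.039 |
| 20 % | 0.302 | 0.060 |
| 30 % | 0.233 | 0.047 |
| 40 % | 0.121 | 0.024 |

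**Step 4: random omission of any number of patients.** At p = 20 % with all ten counted, P(declared safe) = 0.8¹⁰ + 10 × 0.2 × 0.8⁹ = 0.107 + 0.268 = 0.376 (from unrounded terms). If each patient is left out independently of outcome with an assumed probability of 5, 10 or 20 %, this becomes 0.407, 0.438 or 0.495. When several patients are left out, a change away from safe becomes possible but is rare: 0.004 at the 20 % omission rate.

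**Step 5: replacement.** If one patient is replaced after a first dose, eleven are dosed. Counting all of them, two events give 2/11 = 18.2 %, which is safe. If the replaced patient had no event and is not counted, the same two events give 2/10 = 20.0 %, which is not safe. Here it is counting the extra patient that produces the safe verdict, so an all-dosed set alone does not settle how the criterion applies.

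**The case against.** The best defence is that the sentence was never meant as an adherence filter. Ethical aspects uses almost the same phrase for a patient who prefers not to take part, where it can only mean treatment within this trial. In Statistical considerations the stated exclusions are all before treatment. Read together, treated patients are in and untreated patients are out. That reading is reasonable and may well be the intended one. It stands as a reason for moderate confidence. It does not remove the need to say so, because the literal reading is also open and the key phrase is undefined.

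Four stronger readings are tempting, and the documents do not support them.

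- A reader might infer that the plan prescribes a per-protocol safety analysis. It never uses that term; omission is permitted by the wording, not required.
- A reader might infer that toxicity itself pushes patients out of the analysis. Delays, stops for toxicity and stops for corticosteroids follow the protocol's own rules, so they are not in themselves deviations. Those rules concern leaving treatment, not leaving the analysis. A link between omission and toxicity is possible but not shown.
- A reader might infer that events could disappear from the record. They could not: for the primary parameter, "This is done by registration of all adverse events and possible unwanted events that occur in relation to the" treatment, and the final report to the medicines agency must describe all serious events. But registering an event does not place the patient in the numerator or denominator of the verdict.
- A reader might infer that Data registration flatly contradicts the analysis set. That sentence assigns responsibility for analysis and does not set a denominator. The two should read alike, but this is a loose end.

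Nor is there a basis for extending the point to tumour response: it is exploratory, it has no threshold to cross, and the documents give no number of deviating patients.

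**Conclusion.** The ambiguity is real and sits in the primary result. The plan does not state that every vaccinated patient counts towards the under-20 % criterion, and it is silent on patients replaced after one dose. At n = 10, losing one patient changes the conclusion only when exactly two have grade 3-4 events and one of those two is lost; the rate then moves from 20.0 % to 11.1 %, from not safe to safe. No single omission moves it the other way.

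Given one omission, the chance of a changed verdict is about 0.02 to 0.06 if the omitted patient is random, and 0.12 to 0.30 if it is always an event patient, for true rates from 10 to 40 %. These figures assume independent patients and an omission that the documents neither predict nor rule out. Should-fix, moderate confidence.

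**What to change.** In Statistical considerations, replace the sentence that defines the analysis set with:

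> All participants who receive any part of at least one vaccine are included in the safety analysis and in the <20 % criterion, regardless of later deviation, ineligibility, exclusion, withdrawal or replacement; only participants never dosed are left out.

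Add one sentence on how the criterion is applied if replacement takes the number dosed above ten. It should say whether the criterion is a proportion of everyone dosed, in which case two events in eleven pass at 18.2 %, or a fixed number of patients. Then align the sentence on analysis in Data registration with the same set.

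The cost is a short paragraph of protocol wording. No new data, visits or patients are needed, but the change has to be made before the safety results are reviewed.
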